## 7.3 Center Pooling

The Data collected across study sites will be pooled for analysis.

## 7.4 Handling of Missing, Unused, and Spurious Data and Dropouts

All available data for the subjects who are enrolled, received the intended treatments will be included in the data listings and tabulations. Missing data due to incomplete medical records or lost to follow-up will not be imputed for analyses. Therefore, only observed data are analyzed.

## 7.5 Adjustments for Multiple Comparisons

No adjustments for multiple comparisons will be carried out.

## 7.6 Demographic and Other Baseline Characteristics

Demographic and other baseline characteristics will be presented with descriptive statistics. For continuous variables such as age, weight and height, the summary statistics including n, mean, median standard deviation, and minimum and maximum will be summarized. For categorical variables such as gender, frequency and percentage of the subjects in each category will be summarized.

## 7.7 Treatment Characteristics

Data related to surgical procedures, surgery time, blood loss and transfusion, intraoperative cement extravasation / leakage, device models and adverse events/device deficiencies during surgery will be summarized.

## 7.8 Interim Analyses

No interim analysis will be carried out.

## 7.9 Evaluation of Objectives

### 7.9.1 Improvement of ODI from Baseline

The analysis for improvement of ODI at 3 and 12 months from preoperative will be performed. The summary statistic, n, mean, median, standard deviation, maximum and minimum, will be summarized. The improvement of ODI score ( $\mu_{ODI}$ ) of each subject is indicated by baseline score – postoperative score. If  $\mu_{ODI} > 0$ , then ODI is considered to be improved. Otherwise, ODI is not improved. The frequency and percentage of the “improved” and “not improved” subjects will be summarized. The null hypothesis  $H_0$  and the alternative hypothesis  $H_a$  are as follows:

$$H_0: \mu_{ODI} \leq 0$$

$$H_a: \mu_{ODI} > 0$$

The null hypothesis will be rejected if one-sided p-value is less than 0.05 (level of alpha), and the alternative hypothesis will be accepted, indicating that the improvement of ODI score from baseline is significantly greater than zero.

If the data is normal, the paired t-test for the changed score from baseline will be applied in the analysis. The assumption of normality will be assessed by using the Shapiro-Wilks test. If the assumption of normality is not met, analysis will be performed using the non-parametric method, Wilcoxon signed-rank test.

### **7.9.2 Improvement of VAS Back and Leg Pain Score from Baseline**

The improvement of VAS back and leg pain score ( $\mu_{VAS}$ ) of each subject is indicated by baseline score – postoperative score. If  $\mu_{VAS} > 0$ , then VAS back or leg pain is said to be improved. Otherwise, VAS back or leg pain is not improved. VAS back and leg pain scores at preoperative, 3 months and 12 months as well as the changes at 3 months and 12 months from baseline will be summarized. The summary statistic, n, mean, median, standard deviation, maximum and minimum, will be produced. The frequency and percentage of the “improved” and “not improved” subjects will be summarized. The null hypothesis  $H_0$  and the alternative hypothesis  $H_a$  are as follows:

$$H_0: \mu_{VAS} \leq 0$$

$$H_a: \mu_{VAS} > 0$$

The null hypothesis will be rejected if one-sided p-value is less than 0.05, and the alternative hypothesis will be accepted, indicating that the improvement of VAS back and leg pain score from baseline at a specific follow-up visit is significantly greater than zero. The paired t-test for the changed score from baseline will be performed if the distribution of the data is normal, and the Wilcoxon signed-rank test will be carried out if the distribution of the data is not normal.

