## 9.4.2 Back and Leg Pain (VAS)

Levels of back pain and leg pain will be measured using the Visual Analogue Scales (VAS) at baseline (preoperative) and postoperative at 3-month, 12-month and 24-month visits. Subjects will be asked to rate the amount of back pain and leg pain they have had in the last week, where 0 is no pain and 10 is the worst pain possible.

A summary of the data will be based on actual measurements or changes in measurements from baseline (preoperative) to postoperative scores.

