## **11.2 Reporting of Adverse Events**

All adverse events will be considered reportable for this study.

Pain, neurological and function symptoms should be reported as an adverse event when a subject's complaint for any of these symptoms results in an unscheduled visit or when a subject presents with new or worsening pain, neurological and/or function symptoms as compared to the previous visit.

All adverse events will be classified using the following responsibility matrix:

What is Classified	Who Classifies	Classification Parameters
Relatedness	Investigator and Medtronic	Procedure related Device related
USADE potential	Medtronic	USADE
Seriousness	Investigator and Medtronic	SAE/SADE
Diagnosis	Investigator	Based on presenting signs and symptoms and other supporting data

Table 11-2: Event Classification Responsibilities

All reportable events must be recorded from procedure start onwards in the subject's medical record and on the Adverse Event and/or Device Deficiency eCRF and promptly reported to Medtronic. Procedure start for this study is defined as the time when a patient is prepared for the surgery prior to entry to the operating room theater. EC reporting must be completed in accordance with the policies of the governing EC. Regulatory Authority reporting should be in accordance with applicable local regulations.

It is the responsibility of the Investigator to identify the occurrence of adverse events and device deficiencies and to ensure the required information is accurately documented on the eCRF. Reports of adverse events and device deficiencies will include the following information, at a minimum:

- Date of event
- Diagnosis or description of the event
- Assessment of the seriousness and relationship to the device and/or index surgical procedure
- Treatment provided
- Outcome and date of resolution

The clinical course of each adverse event must be followed until resolution, subject discontinuation from the study or last study follow up visit, whichever comes first. "Not resolved" adverse events and device deficiencies must be assessed at each protocol required visit, and new or updated information must be documented on the Adverse Event and/or Device Deficiency eCRF and promptly reported to Medtronic and if applicable to the EC. At time of study exit the status of all unresolved Adverse Events should be evaluated and should reflect subject' status at time of study exit.

#MDT17040SD1703

Version 2.0/ 19 SEP 2018

Page 48 of 65

Medtronic

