## **11.3 Not reportable events**

Examples of events that are not reportable as adverse events for this study are:

- Inability to successfully perform the procedure, unless injury or device deficiency occurs.
- A documented pre-existing condition unless there is a worsening of the nature, severity, duration, or frequency of that condition.
- Pre-planned medical or surgical procedures (e.g., surgery, endoscopy, tooth extraction, transfusion, cosmetic elective surgery); however, the condition leading to the procedures might be a reportable event if there is a worsening of the nature, severity, duration, or frequency of that condition.

Table 11-3 provides a list of expected surgical events. An expected surgical event will not be considered reportable unless it worsens or is present outside the stated timeframe post-procedure.

Event Description	Timeframe from the Surgical Procedure
Anesthesia related nausea / vomiting	24 hours
Low-grade fever (<100°F or 37.8°C)	48 hours
Mild to moderate bruising / ecchymosis	7 days
Seroma	72 hours
Sleep problems (insomnia)	72 hours

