### **7.9.3 Improvement of EQ-5D 5L from Baseline**

The improvement of EQ-5D 5L score ( $\mu_{EQ5D5L}$ ) of each subject is indicated by postoperative score - baseline score. If  $\mu_{EQ5D5L} > 0$ , then EQ-5D 5L is considered to be improved. Otherwise, EQ-5D 5L is not improved. EQ-5D 5L scores at preoperative, 3 months and 12 months as well as the changes at 3 months and 12 months from baseline will be summarized. The summary statistic, n, mean, median, standard deviation, maximum and minimum, will be generated. The frequency and percentage of the “improved” and “not improved” subjects will be summarized. The null hypothesis  $H_0$  and the alternative hypothesis  $H_a$  are as follows:

$$H_0: \mu_{EQ5D5L} \leq 0$$

$$H_a: \mu_{EQ5D5L} > 0$$

The null hypothesis will be rejected if one-sided p-value is less than 0.05 (level of alpha), and the alternative hypothesis will be accepted, indicating that the improvement of EQ-5D 5L score from baseline at a specific follow-up visit is significantly greater than zero. If the data is normal, the paired t-test for the changed score from baseline will be performed in the analysis. If data is not normally distributed, the Wilcoxon signed-rank test will be carried out.

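### Does grouping unchanged and worsened subjects together as not improved (SAP 7.9.1 to 7.9.3) leave a hole in the ODI, VAS and EQ-5D 5L results?

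*SAP*

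**What the plan says.** SAP 7.9.1 to 7.9.3 define improvement so that a positive value is favourable: baseline minus postoperative for ODI and VAS, postoperative minus baseline for EQ-5D 5L. Each section then splits subjects at zero.

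- ODI (7.9.1): "then ODI is considered to be improved. Otherwise, ODI is not improved".
- VAS (7.9.2): "then VAS back or leg pain is said to be improved. Otherwise, VAS back or leg pain is not improved".
- EQ-5D 5L (7.9.3): "then EQ-5D 5L is considered to be improved. Otherwise, EQ-5D 5L is not improved".

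Only these two classes get frequencies and percentages. Each section also plans n, mean, median, SD, minimum and maximum, and a one-sided paired t-test or Wilcoxon signed-rank test at 0.05. For pain the continuous summaries cover "VAS back and leg pain scores at preoperative, 3 months and 12 months as well as the changes at 3 months and 12 months".

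Three other provisions bear on the point.

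- SAP 7.4 plans subject-level output: "All available data for the subjects who are enrolled, received the intended treatments will be included in the data listings and tabulations".
- Protocol 11.2 makes symptoms reportable as adverse events "when a subject presents with new or worsening pain, neurological and/or function symptoms as compared to the previous visit". Among the exclusions from reporting, Protocol 11.3 lists "A documented pre-existing condition unless there is a worsening of the nature, severity, duration, or frequency of that condition", so worsening of an existing condition remains reportable.
- SAP 4 states the objective for all three scores as improvement from baseline. SAP 6 expects around 20 subjects, and SAP 7.1.1 expects two to complete the 12-month visit.

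**The concern.** A subject whose pain is unchanged and a subject whose pain is worse are different clinical results, and the plan puts them in one cell. In a single-arm study meant to evaluate both benefit and safety, a reader will want to know how many patients scored worse after surgery, and no planned table has a row for them. The planned mean, SD and range do not generally supply the number, since a negative minimum shows only that at least one subject deteriorated. If many of the not-improved subjects were in fact worse, the tables would not show it directly.

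A related worry concerns the floor of the pain scale, "where 0 is no pain and 10 is the worst pain possible". The eligibility criteria (Protocol 8.3 and 8.4) set no minimum pain score, and back and leg pain are scored separately. A subject who starts at 0 on one of them can never be classed as improved.

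**Working it through.** There is no plan figure to reproduce, because the point concerns table categories and leaves sample size, alpha and power alone. The check has three parts.

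**1. When do the planned statistics already give the number worsened?** Let k be the number not improved and m the minimum change (positive is favourable). Both are planned outputs.

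- m ≥ 0: nobody worsened.
- k = 0: nobody worsened.
- k = 1: that subject holds the minimum, so the sign of m settles it.
- Two subjects at a visit, as expected at 12 months: the minimum and maximum are the two change scores, so everything is known.
- k ≥ 2 and m < 0: the number worsened lies between 1 and k, and sign information alone does not fix it.

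Only the last case is ambiguous, and it is realistic only at 3 months.

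**2. How wide can the ambiguity be?** Two constructed sets of (baseline, postoperative) VAS scores, 20 subjects each, assuming whole-number scoring:

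- Set A: (1,1) (4,3) (5,7) (6,2) (6,3) (6,5) (7,3) (7,7) (8,1) (8,1) (8,2) (8,2) (8,8) (9,2) (9,4) (9,8) (9,9) (10,4) (10,4) (10,10)
- Set B: (1,2) (4,1) (5,2) (6,1) (6,7) (6,8) (7,2) (7,2) (8,1) (8,4) (8,5) (8,8) (8,9) (9,3) (9,3) (9,3) (9,10) (10,4) (10,4) (10,7)

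| Quantity | Set A | Set B |
|---|---|---|
| Baseline mean, median, SD, range | 7.4, 8, 2.257, 1 to 10 | same |
| Postoperative mean, median, SD, range | 4.3, 3.5, 2.867, 1 to 10 | same |
| Change mean, median, SD, range | 3.1, 3.5, 3.007, −2 to 7 | same |
| Improved / not improved | 14 / 6 | 14 / 6 |
| Unchanged | 5 | 1 |
| Worsened | 1 (5%) | 5 (25%) |
| Shapiro-Wilk p for the change | 0.018 | 0.009 |
| Wilcoxon W+ (zeros dropped) | 116 on 15 pairs | 175 on 19 pairs |
| One-sided Wilcoxon p | about 0.0007 | about 0.0006 |

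The planned descriptive tables cannot tell the sets apart. The planned test can in part. At a 0.05 normality cutoff (the SAP names none) both sets go to Wilcoxon, and the statistics differ. The number of non-zero pairs would reveal the tie count, though the SAP does not promise to print it. The example shows what is possible and forecasts nothing.

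**3. How large is it for ODI?** Protocol 13.2 plans on a mean 12-month improvement of 10 and SD 24. Assume a normal change recorded in 2-point steps (the step is an assumption), so that unchanged means between −1 and +1:

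- Improved: 1 − Φ((1 − 10)/24) = 1 − Φ(−0.375) = 0.646
- Worsened: Φ((−1 − 10)/24) = Φ(−0.458) = 0.323
- Unchanged: 1 − 0.646 − 0.323 = 0.030 to three decimals before rounding of the parts
- Worsened share of not improved: 0.323/0.354 = 0.914
- Unchanged in 20 subjects, Binomial(20, 0.0305): P(0) = 0.539 and P(at most 1) = 0.877

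Under these assumptions about 91% of not-improved ODI subjects are worse, so the two-way table already comes close to showing deterioration. Applying 12-month figures to 3 months is an extrapolation.

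**What a third row would alter.** Splitting the not-improved class moves nobody into or out of the improved class. The improved percentage, the change scores and every test stay as they are.

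**The case for a change.** The best argument for acting is that the cost is trivial: one sentence in each of three sections and a few table rows, from data already collected. How many scored worse is a basic question in a small single-arm study, and SAP 7.9.4 already gives leakage three classes instead of two. The listings hold the data but are not a planned count. Adverse event reporting rests on unscheduled visits or on symptoms judged against the previous visit, so it does not measure score change from baseline, and it does not cover a fall in EQ-5D 5L as such.

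All of that is accurate, and it stands as a reason a report author might show the split. It does not make the plan wrong. No protocol or SAP statement promises a count of worsened scores, and improved versus not improved answers the stated objective directly. A hand count over about 20 listed subjects takes minutes.

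The size of the gain is also uncertain. It depends on ties, for which the documents give no rate. Pain recorded more finely than whole numbers would have fewer ties than the example, and Protocol 9.4.2 does not say scores are whole numbers. No magnitude is available for EQ-5D 5L.

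The floor issue is weaker. Its frequency is unknown, the planned preoperative minimum would show whether any subject started at 0, and a second denominator is not worth planning for an event nobody has shown to occur.

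**Conclusion.** No change to the plan follows. The observation is right as far as it goes: no planned table counts worsened subjects, and at 3 months, if at least two subjects are not improved and the minimum change is negative, the descriptive tables will not show how many deteriorated. In the constructed pain example that leaves 5% and 25% worsened indistinguishable. But nothing inferential depends on it, the improved percentage is unaffected, at 12 months the expected two subjects are fully described by their minimum and maximum, and the listings contain the answer for everyone else. For ODI the pooling is close to harmless under a normal change with mean 10, SD 24 and 2-point steps. The conclusion rests on the expected sample of around 20 and on the listings being produced as SAP 7.4 says. Analysts can add unchanged and worsened counts to the 3-month tables if they wish; that is reporting style and needs no amendment.

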## 8.3 Inclusion Criteria

A subject must meet the following inclusion criteria to participate in this trial:

- 1. One or more of the following diagnostic indications:
  - Degenerative Spinal Disease (e.g. degenerative disc disease, spondylolisthesis and/or spinal stenosis)
  - Deformity (e.g. degenerative deformity)
- 2. Degenerative Spinal Disease patients only: Patient has been unresponsive to non-operative treatment for at least three months or has progressive symptoms or signs of nerve root/spinal cord compression while undergoing continued non-operative management.
- 3. Compromised bone quality defined as a hip DXA scan T-score less than or equal to -1.0 or spine quantitative CT (qCT) actual volumetric bone mineral density threshold of  $\leq$  120 mg/cm^3.
- 4. Requires a procedure with an instrumented, posterior thoracic and/or lumbar spinal stabilization and/or immobilization.
- 5. Is scheduled to receive a construct using CD Horizon® Spinal System components with at least one Fenestrated Screw cemented with Fenestrated Screw Cement.
- 6. At least 22 years old or greater at the time of informed consent.
- 7. Is able to understand and willing to sign the Patient Informed Consent Form.
- 8. Is willing and able to undergo the study procedure and perform the follow up visits.

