### **7.1.3 Analysis Datasets**

Analysis will be conducted for the subjects who are enrolled in the trial, undergo the designated surgical procedure, and receive the treatment of the CD HORIZON® Fenestrated Screw Spinal System with Fenestrated Screw Cement. The subjects who are enrolled but do not receive intended medical devices (such as competitor's screws and/or cement) will not be included in analysis. The missing data will not be imputed, and all analyses will be based on the observed data. For the subjects who already had a data collection beyond 3 months at time of the premature termination announcement, the data from beyond 3 months will be summarized. For those who enrolled and underwent surgery but will not be able to complete 3-month follow-up visit by the scheduled study closure, the data, if available, will be included in the analysis.

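### SAP 7.9.2 puts a subject with no back or leg pain before surgery in the 'not improved' class, whatever the outcome, and pools those still pain-free with those unchanged in pain or worse

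*SAP*

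**What the plan says.** SAP 7.9.2 defines VAS improvement as a difference that "of each subject is indicated by baseline score – postoperative score". If that difference is above 0, "then VAS back or leg pain is said to be improved". All remaining subjects fall into one class: "Otherwise, VAS back or leg pain is not improved". The table is then specified as follows: "The frequency and percentage of the “improved” and “not improved” subjects will be summarized". There is no third class for no change, and none for subjects without the symptom at baseline.

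Protocol 9.4.2 describes the scale as one "where 0 is no pain and 10 is the worst pain possible".

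On who is counted, SAP 7.1.3 states: "Analysis will be conducted for the subjects who are enrolled in the trial, undergo the designated surgical procedure", with receipt of the study device as the remaining condition. SAP 7.4 adds: "Therefore, only observed data are analyzed". Neither section mentions baseline pain.

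On who may enter, Protocol 8.3 lists two indications. The first reads "Degenerative Spinal Disease (e.g. degenerative disc disease, spondylolisthesis and/or spinal stenosis", closing the bracket there; the second is deformity. Protocol 8.3 and 8.4 set no minimum VAS score. The requirement of failed non-operative care or progressive nerve compression applies only to the degenerative group, and either alternative is enough.

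**The concern.** The rule gives one label to three different outcomes: no symptom before or after surgery, a symptom that did not change, and a symptom that appeared or got worse. The first of these is not a poor result, yet the table cannot tell it from the other two.

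The documents allow such subjects to enter. Protocol 6.2 and 7.5 describe degenerative disc disease as back pain of discogenic origin, so a subject may have back pain and no leg pain. Deformity subjects need no pain at all to qualify.

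The plan treats a comparable situation differently elsewhere. Under Protocol 9.4.4, a neurological element that stays the same counts towards success, so a normal finding that remains normal is not held against the subject.

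What is at stake is how a descriptive percentage is read. As defined, it depends both on how many subjects had the symptom at entry and on what happened to those who had it. The SAP version history shows that the two classes and their summary were added in version 2.0, when the expected number of subjects was about 20.

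**Working it through.** The plan states no expected percentage improved, so there is no figure to reproduce. The check covers the rule and then its arithmetic.

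**Inputs from the documents**
- Change = baseline - postoperative; improved only if change > 0 (SAP 7.9.2).
- VAS from 0 to 10, with 0 as no pain (Protocol 9.4.2).
- All treated subjects with observed data are counted (SAP 7.1.3 and 7.4). An observed 0 is not missing, so it stays in.
- About 20 subjects available (SAP 6); two expected at 12 months (SAP 7.1.1).

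**Assumed, not in the documents**
- k, the number of subjects with baseline 0 on the scale concerned: 0 to 8 of 20 is shown.
- I, the number improved: illustrative values only.
- Back and leg pain are classed separately, as the 'back or leg' wording in SAP 7.9.2 suggests.

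**Step 1: the rule at baseline 0.** Change = 0 - postoperative. Since the postoperative score is at least 0, the change is at most 0. Running through postoperative scores from 0.0 to 10.0 gives no case classed as improved.

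**Step 2: effect on the percentage.** All I improved subjects come from the n - k with baseline above 0.
- SAP percentage = I/n.
- Percentage among subjects with the symptom at baseline = I/(n - k).
- Hence I/n = [I/(n - k)] x (1 - k/n), and the SAP percentage cannot exceed 1 - k/n.

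The two percentages differ only if k is at least 1 and at least one subject improves. With I = 0, both are 0.

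**Step 3: size with n = 20.** Each baseline-0 subject lowers the ceiling by 1/20 = 5 points.

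| k | Highest possible SAP percentage |
|---|---|
| 0 | 20/20 = 100% |
| 1 | 19/20 = 95% |
| 2 | 18/20 = 90% |
| 4 | 16/20 = 80% |
| 6 | 14/20 = 70% |
| 8 | 12/20 = 60% |

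In every row, the percentage among subjects with the symptom would be 100%.

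Examples where not everyone improves:
- I = 14, k = 2: 14/20 = 70.0% against 14/18 = 77.8%.
- I = 14, k = 4: 14/20 = 70.0% against 14/16 = 87.5%.
- I = 12, k = 5: 12/20 = 60% against 12/15 = 80%.

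At 12 months with n = 2, one baseline-0 subject would cap the SAP percentage at 1/2 = 50%.

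**The case against.** The best defence is that the label is literally true. A subject at 0 before and after surgery has not improved, and the SAP never calls this class failure or non-response. The share improved among all treated subjects is a legitimate summary. This stands: the reported figure is low only relative to a different quantity, the share among subjects who had the symptom. It does not answer the complaint that one class mixes pain-free subjects with unchanged and worse ones.

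The number affected is also unknown. The only preoperative back and leg VAS figures in the documents come from a cited stenosis cohort of 37 (Protocol 4.1), with means of 7.87 ± 0.95 for back and 8.82 ± 0.83 for leg. Zeros would be rare in such a cohort. That population is narrower than this one, so it does not rule zeros out here, but nothing in the documents supports a large k either.

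Some of the information will be available anyway. The planned minimum would reveal a baseline of 0, and SAP 7.4 provides for listings from which k could be counted. That helps, but it leaves the split to be chosen after the results are seen.

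The same rule counts any fall in score, however small, as improvement. That is a separate leniency in the other direction, and it does not repair the mixed class. Baseline-0 subjects also pull the mean change towards or below zero, but a mean over all subjects does not label anyone.

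A reader might go further and infer that comparisons of back with leg pain, or of degenerative with deformity subjects, will be distorted, or that the efficacy conclusion is at risk. The documents do not support this. No such comparison is planned: SAP 7.2.2 provides only for subgroup summaries where appropriate. The one-sided test in SAP 7.9.2 uses the change scores, and no success threshold is attached to the percentage.

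**Conclusion.** The point holds as a defect in a stated classification rule. A subject with baseline 0 on the back or leg scale cannot be classed as improved, and one who stays pain-free is grouped with subjects who are unchanged in pain or worse. Relative to the percentage among subjects with the symptom at baseline, the reported percentage is scaled by (1 - k/n), which is 5 points off the ceiling per such subject when n is 20.

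This rests on separate classification of back and leg pain and on at least one improved subject. The actual size is unknown: k is not given and may be 0, in which case nothing changes. It would be wrong to conclude that the percentage in this cohort will be too low, or that a test or decision depends on it. The change is worth making because it is cheap and can be fixed before the tables are run.

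**What to change.** In SAP 7.9.2:
- State that back pain and leg pain are classified separately.
- Report the number and percentage improved among subjects with a baseline score above 0 on the scale concerned. The all-subject percentage may be kept beside it.
- Show subjects with baseline 0 in their own row, split into still no pain and new pain, so that new postoperative pain stays visible.
- Keep the mean change in all subjects, and the test on it, as planned.

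The cost is one sentence in the SAP and one more row per table, from data already collected. The drawback is a smaller, and so less precise, denominator for the percentage among subjects with the symptom.
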